5.3.2. Pre-Infusion Visit (Day -1)

Participants enrolled based on the screening data will arrive to the hospital within 24 hours prior to gene transfer.

They will undergo the following evaluations:

- Adverse events
- Physical Examination
- Vital signs (temperature, respiratory rate, heart rate, blood pressure)
 - Weight
- Concomitant medications
- Prophylactic enteral prednisone or prednisolone will be started
- Labs will be obtained, including
 - CBC and differential
 - Electrolytes
 - Serum/plasma total protein

- Albumin
- PT, PTT, INR
- Creatinine/BUN
- AST, ALT, serum/plasma GGT
- Alkaline phosphatase
- Amylase
- Serum/plasma total bilirubin
- Random glucose
- Troponin

In previous gene therapy studies, antigen-specific T-cell response to the AAV9 vector have been reported (Mingozzi and High, 2011). This is an expected response between 2 - 12 weeks following gene transfer. One possible consequence of such antigen-specific T-cell responses is clearance of the transduced cells and loss of transgene expression.

In order to reduce the risk of the host immune response to our AAV9-based therapy, participants will be started on prophylactic enteral prednisone or prednisolone (glucocorticoid) (approximately 1 mg/kg/day) one day prior to the gene transfer and only after passing all inclusion and exclusion criteria (in the event that a measure is repeated on Day -1). This will be continued after gene transfer as discussed in Section 5.5.1.

Prophylactic enteral prednisone or prednisolone will not be provided by the Sponsor; the standard of care at the site/country should be used for prophylaxis.

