6. SAFETY

The Investigator or site staff is responsible for detecting, documenting and reporting events that meet the definition of an adverse event (AE) or a serious adverse event (SAE). All AEs (serious and not serious) occurring during the observation period established in this protocol must be documented. All adverse events will be followed until resolution or stabilization.

The study period during which adverse events must be reported is defined as the period from signature of the informed consent to the end of the study treatment follow-up. For this study, the study treatment follow-up is defined as 24 months following the administration of study treatment and is considered the Final Visit for each participant. The Principal Investigator will adhere to any other SAE reporting requirements in accordance with national regulations, local laws, and the national institutional policies and procedures, as applicable. The Principal Investigator will be responsible for ensuring that the reporting requirements are fulfilled and will be held accountable for any reporting lapses.

It is important to note that for this clinical trial, Principal Investigators should only report the following AEs:

- All Grade 2 or greater AEs
- Grade 1 AEs considered by the Principal Investigator as clinically significant, independent of the association or relatedness to the study agent
- Grade 1 AEs assessed by the Principal Investigator as possibly, probably or definitely related to the study agent

Abnormal laboratory findings should be recorded as AEs when judged by the Principal Investigator/Sub-Investigator as clinically significant. Special attention should be considered for changes in AST/ALT, platelets and amylase.

There are no drug comparators used in this study, so there is only one Investigational Medicinal Product to assess the causality/expectedness evaluation, the gene therapy vector described in the Investigational Brochure.

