8.1.3 Handling of Multiple Observations

For efficacy data, if multiple records were recorded for the same protocol-defined visit, the re-assayed data will be used for data summary and analysis. Re-assayed data from unscheduled visits will be treated similarly.

If a subject has a scheduled visit, the assessment obtained at the scheduled visit will be used for data summary and analysis. Otherwise, if no scheduled visit assessment exists but at least one unscheduled visit assessment is available within the protocol-defined visit window, then the data at the latest unscheduled visit within the protocol-defined visit window will be used for data summary and analysis.

Any unscheduled visits that cannot be attributed to a scheduled visit according to a protocoldefined visit window will not be included in descriptive statistical summaries but will be presented in listings.

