8.3.2 Clinical Laboratory Evaluations

Hematologic, chemistry, coagulation and urinalysis laboratory measurements will be summarized by visit. For the continuous data, descriptive statistics (n, mean, SD, median, minimum, maximum) in change (absolute and percent) will be presented. For the categorical data, the number and the percentage of subjects for each observed category under each analyte will be summarized.

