8.3.4 Electrocardiogram (ECG) and Echocardiogram

Electrocardiogram

The following ECG measurements are taken in 12-lead ECG at Screening/Visit 1, Visit 8 (Day 90), Visit 9 (Day 180), Visit 10 (Month 12):

• Overall evaluation (normal; abnormal-clinically significant; abnormal-not clinically significant).

The number and percentage of individuals on overall evaluation with normal, abnormal-not clinically significant, abnormal-clinically significant ECG's results will be tabulated.

All reported abnormal values will be listed.

Echocardiogram

The following measurements are taken at Screening/Visit 1, Visit 8 (Day 90), Visit 9 (Day 180), Visit 10 (Month 12):

- Fractional shortening %
- LV Ejection fraction %
- Overall evaluation (normal; abnormal-clinically significant; abnormal-not clinically significant)

For the continuous data, descriptive statistics (n, mean, standard deviation, median, minimum, maximum) in raw and change (absolute and percent) will be presented.

The number and percentage of individuals on overall evaluation with normal, abnormal-not clinically significant, abnormal-clinically significant results will be tabulated.

All reported abnormal values will be listed.

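### Laboratory safety is tabulated only as by-visit change, so an AST/ALT rise or platelet fall seen only at an unscheduled draw reaches no laboratory table

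*SAP*

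**What the plan says.** **Laboratory tables.** SAP 8.3.2 states: "Hematologic, chemistry, coagulation and urinalysis laboratory measurements will be summarized by visit". For continuous tests, "descriptive statistics (n, mean, SD, median, minimum, maximum) in change (absolute and percent) will be presented". For the rest: "For the categorical data, the number and the percentage of subjects for each observed category under each analyte will be summarized". The section defines no worst post-baseline value, no toxicity grade and no shift from baseline. By contrast, SAP 8.3.4 presents continuous echocardiogram results "in raw and change (absolute and percent) will be presented".

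**Unscheduled values.** Under SAP 8.1.3 a scheduled assessment is used whenever there is one. If there is none, but an unscheduled one falls in the window, "then the data at the latest unscheduled visit within the protocol-defined visit window will be used for data summary and analysis". Unscheduled visits that fit no window "will not be included in descriptive statistical summaries but will be presented in listings". SAP 8.1 and 8.1.1 confirm that the listings hold all data, scheduled and unscheduled.

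**Adverse event route.** Protocol 6 says: "Abnormal laboratory findings should be recorded as AEs when judged by the Principal Investigator/Sub-Investigator as clinically significant". The same paragraph singles out AST/ALT, platelets and amylase for particular attention. Protocol 6.2 grades adverse events by CTCAE v4.03, and SAP 8.3.1 tabulates treatment-emergent events by severity.

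**The concern.** Product safety is one of the primary endpoints (SAP 4.1), and the protocol ties the steroid taper to AST, ALT and ELISpot results (Schedule of Evaluations, note 4). It is therefore reasonable to expect the report to show, for each child, how far the key tests moved at their worst. The planned tables answer a different question: how the group had changed at each nominal visit. An out-of-schedule draw may hold a child's most extreme value, and the summary rule sets such draws aside.

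Reporting change alone has a second cost. Exclusion criterion 17 (Protocol 4.2.2) lists GGT and bilirubin but not AST or ALT, so a child may enter with raised transaminases. A change from baseline does not show what level that child reached.

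At stake is whether a reader of the laboratory tables can rely on them to show each child's extremes, or must search the listings.

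**Working it through.** The plan gives no figure on this point to reproduce. The check has three parts: where a value can go, how many days the rule affects, and what the tables would show.

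**1. Where an extreme laboratory value can appear**

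- Measured at a scheduled visit: in the by-visit table, including its minimum and maximum change.
- Unscheduled, in a window, with a scheduled value present: not in the table.
- Unscheduled, in a window, with no scheduled value: in the table if it is the latest such value.
- Unscheduled, outside every window: not in the table.

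All four go to listings. Any of them becomes an adverse event if judged clinically significant.

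**2. Days outside scheduled windows**

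Inputs are the visit days and windows in the Protocol Schedule of Evaluations. The reference period is Days 14-84, taken from Protocol 5.3.2, which says of T-cell responses to the vector: "This is an expected response between 2 - 12 weeks following gene transfer". Length: 84 - 14 + 1 = 71 days.

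Liver tests (AST, ALT, GGT), days covered within the period:

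- Day 14 ± 2: Days 14-16 = 3
- Day 30 ± 3: Days 27-33 = 7
- Day 45 ± 3: Days 42-48 = 7
- Day 60 ± 7: Days 53-67 = 15
- Day 75 ± 3: Days 72-78 = 7
- Day 90 ± 7: Days 83-84 = 2

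Covered: 3 + 7 + 7 + 15 + 7 + 2 = 41. Uncovered: 71 - 41 = 30 (42%). The runs are Days 17-26, 34-41, 49-52, 68-71 and 79-82 (10 + 8 + 4 + 4 + 4 = 30).

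The floating draw two weeks after steroids is not counted. With a taper from about Day 60 lasting at least 4 weeks, its window opens no earlier than about Day 60 + 28 + 14 - 7 = Day 95.

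Platelets come with the blood count, which in this period is scheduled only at Days 14, 30 and 90. Covered: 3 + 7 + 2 = 12. Uncovered: 71 - 12 = 59 (83%), including an unbroken run of 49 days (Days 34-82).

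Later gap, both tests: the Day 180 ± 21 window ends at Day 201.

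- Month 12 = Day 360 (the 30-day month of SAP 7.6): window opens at Day 330; gap Days 202-329 = 128 days.
- Month 12 = Day 365: window opens at Day 335; gap Days 202-334 = 133 days.

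**3. What the tables would show (assumed values, 5 children)**

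- AST changes at one scheduled visit of 0, 5, -3, 2 and 400 U/L: mean 404/5 = 80.8, median 2, maximum 400. The extreme is visible.
- The 400 occurs at an unscheduled draw and that child's scheduled change is 4: mean 8/5 = 1.6, median 2, maximum 5. The extreme is absent.

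**The case against.** **Listings and sample size.** Nothing is lost: every value is in the by-subject listings, and five children's results can be read directly. Most secondary efficacy endpoints are listing-only as well (SAP 8.2.2). This stands, and it is the main reason the severity is low. A listing still does not give a graded summary.

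**Adverse event tables.** A marked abnormality should be recorded as an adverse event, graded by CTCAE and tabulated by severity. The time bands in SAP 8.3.1 run from treatment to onset, so they have no gaps between visit windows, and all adverse events are reviewed medically before database lock. This largely stands, but it depends on the investigator judging the finding clinically significant.

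**Scope of SAP 8.1.3.** Its first paragraph is limited to efficacy data. The paragraphs on scheduled and unscheduled visits carry no such limit, so applying them to laboratory data is the natural reading, though not an explicit one. If they were not meant to apply, the SAP has no rule for unscheduled laboratory values and needs one.

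**Stronger readings that the documents do not support**

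- That laboratory data are shown only as means, so that any peak is averaged away. Median, minimum and maximum are planned; with 5 children the by-visit extreme is one child's value.
- That 42% or 83% is the chance of missing an event. The documents give no number of unscheduled draws. For liver tests the longest uncovered run in Days 14-84 is 10 days, so a sustained rise would also be sampled at a scheduled visit, though perhaps not at its peak.
- That unscheduled draws are always prompted by abnormal results, or that the latest one in a window follows recovery. Either is plausible; neither is stated.
- That 2-12 weeks is a liver-injury window. Protocol 5.3.2 gives it for T-cell responses and names loss of transgene expression as a possible consequence. Protocol 3.3 likewise justifies steroids by sustained expression. Here it serves only as a reference period.

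**Conclusion.** The point holds as a gap in reporting. Under SAP 8.3.2 and 8.1.3 together, an AST/ALT rise or platelet fall found only at an unscheduled draw enters no laboratory table, unless that draw stands in for a missing scheduled value in its window. No worst-value, grade or shift summary is planned that would recover it.

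The day counts measure the calendar span over which an unscheduled value would be left out for falling outside every window. In-window values displaced by a scheduled one come on top. The counts do not estimate how many values, or which children, are affected.

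The conclusion assumes that the unscheduled-visit paragraphs of SAP 8.1.3 apply to safety data and that raw laboratory values, which SAP 8.3.2 does not name, are not tabulated. The counts also assume nominal windows measured from Day 0. Severity is minor to modest: 5 children, complete listings and CTCAE-graded adverse event tables limit the harm. The case for acting is that the remedy is cheap.

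**What to change.** - **SAP 8.1.3:** state whether the unscheduled-visit rule covers safety data, and limit the exclusion to by-visit tables.
- **SAP 8.3.2, existing tables:** present raw values as well as absolute and percent change, as is done for the echocardiogram.
- **SAP 8.3.2, one new table, per child and overall, from all scheduled and unscheduled post-baseline values:** worst value (maximum; minimum for platelets) and worst CTCAE v4.03 grade, with shift from baseline grade, for ALT, AST, GGT, bilirubin, platelets, creatinine and amylase. For troponin, give the maximum multiple of the upper limit of normal.

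The cost is one extra table from data already collected, with no new procedures. The reported worst values will look less favourable than by-visit summaries. A child sampled more often also has more chances of an extreme value, so the number of draws per child should be shown beside it.

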8.3.3 Vital Signs and Physical Examination

Vital Signs

Vital signs will include weight, height, BMI, head circumference, body temperature, heart rate, respiratory rate, pulse oximetry, and systolic and diastolic blood pressure for all time

points. Summary statistics will be calculated at baseline and follow-up time points as well as the nominal and percent changes from baseline for each visit.

Physical Exams

Adverse physical examination changes are captured as AEs. Physical Exam findings and vital signs will be included in the listings. Physical exam findings will be listed at each visit.

8.3.4 Electrocardiogram (ECG) and Echocardiogram

Electrocardiogram

The following ECG measurements are taken in 12-lead ECG at Screening/Visit 1, Visit 8 (Day 90), Visit 9 (Day 180), Visit 10 (Month 12):

• Overall evaluation (normal; abnormal-clinically significant; abnormal-not clinically significant).

The number and percentage of individuals on overall evaluation with normal, abnormal-not clinically significant, abnormal-clinically significant ECG's results will be tabulated.

All reported abnormal values will be listed.

Echocardiogram

The following measurements are taken at Screening/Visit 1, Visit 8 (Day 90), Visit 9 (Day 180), Visit 10 (Month 12):

- Fractional shortening %
- LV Ejection fraction %
- Overall evaluation (normal; abnormal-clinically significant; abnormal-not clinically significant)

For the continuous data, descriptive statistics (n, mean, standard deviation, median, minimum, maximum) in raw and change (absolute and percent) will be presented.

The number and percentage of individuals on overall evaluation with normal, abnormal-not clinically significant, abnormal-clinically significant results will be tabulated.

All reported abnormal values will be listed.

8.4 Definitions and Derived Variables

8.4.1 Chronological Age

Chronological Age (months) will be calculated using the Date of Birth and the testing date.

Chronological Age = (Testing Date - Date of Birth + 1) / 30

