4.2. Inclusion/Exclusion Criteria

4.2.1. Inclusion Criteria

1. Diagnosis of MPS IIIA confirmed by the following methods:
 - a. No detectable or significantly reduced SGSH enzyme activity by leukocyte assay, and
 - b. Genomic DNA analysis demonstrating homozygous or compound heterozygous mutations in the SGSH gene
2. Cognitive Development Quotient (DQ) lower than 60 (calculated by Bayley Scales of Infant and Toddler Development - Third Edition)
3. Must be ambulatory, though may receive assistance with ambulation
4. Age range of 2 years up to 18 years (excluded).

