8.4.3 Mullen Developmental Age (DA) and Developmental Quotient (DQ)

Mullen Developmental Age (in months) is calculated as the mean of the age equivalents obtained from the scores of four out of the five domains of the scale except Gross motor.

Mullen DA = (Fine Motor Age Eq + Receptive Language Age Eq + Expressive Language Age Eq + Visual Reception Age Eq) / 4

Mullen DQ = (Mullen DA / Chronological Age) * 100

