8.4.4 Vineland Adaptive Age Equivalent and Adaptive Developmental Quotient (DQ)

Vineland Adaptive Developmental (in months) is calculated using the Age Equivalents from the 11 subdomains of the scale. Instead of using the mean of the 11 subdomains, the subdomains are first grouped into four areas, and the Adaptive Age Equivalent is calculated from the mean of those four areas. Example:

- Communication Age Equivalent is calculated as the mean of: Receptive Age Eq + Expressive Age Eq + Written Age Eq
- Daily living skills Age Equivalent is calculated as the mean of: Personal Age Eq + Domestic Age Eq + Community Age Eq
- Socialization Age Eq is calculated as the mean of: Interpersonal relationships Age Eq + Play and Leisure Time Age Eq + Copying Skills Age Eq
- Motor Skills Age Eq is calculated as the mean of: Fine Age Eq

Vineland Adaptive Age Equivalent = (Communication Age Eq + Daily living skills Age Eq + Socialization Age Eq + Motor Skills Age Eq) / 4

Vineland DQ = (Vineland Age equivalent / Chronological Age) * 100

The Vineland Adaptive AE and Adaptive DQ scores will be collected through Case Report Forms (CRF) and will not be recalculated during programming.

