8.4.5 Cognitive Bayley Developmental Age (DA) and Cognitive Developmental Quotient (DQ)

Mean Developmental Age (DA) = (Developmental Age for Cognitive + Developmental Age for Receptive Language + Developmental Age for Expressive Language + Developmental Age for Fine Motor) / 4

Cognitive DQ = (Cognitive Developmental Age / Chronological age) *100

| 8.4.6 | CCI |
|-------|-----|
| | |
| | |
| | |
| | |
| ٠ | CCI |
| ٠ | |
| • | |
| • | |
| • | |
| • | |
| | |
| CCI | |

DQ = (Mean Developmental Age/ Chronological age) *100

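### SAP 8.4.1 counts a month as 30 days, so chronological age is about 1.5% too high and the DQs derived from it about 1.5% too low (minor)

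*SAP*

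**What the plan says.** SAP 8.4.1 gives the unit and the inputs: "Chronological Age (months) will be calculated using the Date of Birth and the testing date". The formula follows: "Chronological Age = (Testing Date - Date of Birth + 1) / 30".

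The result is the denominator of three quotients that the SAP defines:

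- SAP 8.4.3: "Mullen DQ = (Mullen DA / Chronological Age) * 100"
- SAP 8.4.5: "Cognitive DQ = (Cognitive Developmental Age / Chronological age) *100"
- SAP 8.4.6 (partly redacted): "DQ = (Mean Developmental Age/ Chronological age) *100"

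SAP 8.4.4 defines the Vineland quotient with the same denominator, "Vineland DQ = (Vineland Age equivalent / Chronological Age) * 100", but adds that the Vineland scores come from the CRF and are not recomputed. Sections 8.4.3 and 8.4.5 contain no such exemption.

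On the numerator, SAP 8.4.3 says: "Mullen Developmental Age (in months) is calculated as the mean of the age equivalents". SAP 8.4.4 also works in months. The visible text of 8.4.5 gives no unit for the Bayley developmental age, and the numerator definition in 8.4.6 is redacted.

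**The concern.** A developmental quotient is a ratio of two ages, so both must be in the same unit. Twelve 30-day months make 360 days, so under this rule each year of life counts as 365.25/30 = 12.175 months. If the age equivalents are in ordinary calendar months, the denominator is inflated and the numerator is not. Every quotient derived this way is then too low, always in the same direction, and changes from baseline shrink towards zero. A 10-year-old whose age equivalent is exactly 120 months would score 98.5 instead of 100.

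There is also a question of consistency. The Vineland DQ is taken from the CRF. If the CRF uses calendar months, a child's Vineland DQ and Mullen or Bayley DQ at the same visit would rest on two different ages.

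**Working it through.** The documents contain no worked age or DQ, so there is no figure of the plan's own to reproduce. The check applies the formula over the protocol's age range.

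**Inputs**

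- Formula: (days + 1)/30, from SAP 8.4.1.
- Age range: 2 to under 18 years, from Protocol 4.2.1.
- DQ range: below 60, from Protocol 4.2.1.
- Mean calendar month: M = 365.25/12 = 30.4375 days. This is an assumption, not a figure in the documents.

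**Formulas**, for a true age of m calendar months

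- SAP age = (m × 30.4375 + 1)/30
- Age error = SAP age/m − 1
- DQ factor = m/SAP age

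**Results**

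| True age | SAP age (months) | Excess (months) | Age error | DQ factor | DQ error | True DQ 30 becomes | True DQ 60 becomes |
|---|---|---|---|---|---|---|---|
| 2 y (24) | 731.5/30 = 24.383 | 0.38 | +1.60% | 0.98428 | −1.57% | 29.53 | 59.06 |
| 10 y (120) | 3653.5/30 = 121.783 | 1.78 | +1.49% | 0.98536 | −1.46% | 29.56 | 59.12 |
| 18 y (216) | 6575.5/30 = 219.183 | 3.18 | +1.47% | 0.98548 | −1.45% | 29.56 | 59.13 |

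**Split of the error.** The divisor alone gives 30.4375/30 − 1 = +1.46% in age and −1.44% in DQ at every age. The added day supplies the rest. At age 2 it is 1/730.5 = 0.14%, and at age 18 it is 1/6574.5 = 0.015%.

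**Change from baseline.** Take a true fall from DQ 40 at 60 months (age equivalent 24) to DQ 35 at 72 months (age equivalent 25.2), a change of −5.00.

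- SAP age at 60 months = 1827.25/30 = 60.908, so DQ = 100 × 24/60.908 = 39.40
- SAP age at 72 months = 2192.5/30 = 73.083, so DQ = 100 × 25.2/73.083 = 34.48
- Computed change = −4.92

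**Sensitivity**

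- With a 365-day year (30.4167 days per month), the DQ error is 1.39% to 1.51%.
- With exact calendar dates (mid-June births, 2000 to 2011), it is 1.51% to 1.64% at age 2 and about 1.45% to 1.46% at age 18. At a true DQ of 60, the largest of these is 60 × 0.0164 = 0.98 points.
- If age equivalents were themselves in 30-day months, only the added day would remain, a shift of under 0.15%.

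**The case against.** The strongest reply is that this is a declared convention and not a slip. SAP 7.6 also treats a month as thirty days and counts days inclusively when it reports study duration, so 8.4.1 follows the same reproducible rule. That explains where the formula may have come from, but it does not justify it here. Section 7.6 sorts follow-up into broad categories, where 1.5% rarely matters. Section 8.4.1 feeds a ratio against an age equivalent, where the units must match.

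The second reply is that the bias depends on an unverified assumption about the age equivalents. This is correct as far as it goes. The SAP says only that the Mullen and Vineland ages are in months, it shows no unit for the Bayley age, and the 8.4.6 numerator cannot be seen. The size of the bias is therefore conditional. Nothing in the SAP, however, suggests that age equivalents use 30-day months.

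The third reply is that no visible result changes. This largely stands:

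- SAP 4.1, 4.2, 8.2.1 and 8.2.2 list no DQ endpoint.
- There are 5 subjects, no interim analysis and no visible hypothesis test, and SAP section 10 drops the natural history comparison.
- The error is almost the same proportion at all ages, so direction and ranking are essentially preserved.
- A true DQ from 60 to about 60.9 would be computed as below the entry limit of 60, but the documents do not say that eligibility used this formula.

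These points limit the importance of the error. They do not make the formula right.

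**Conclusion.** The concern holds and is minor. As written, the rule overstates age by 1.47% to 1.60% over ages 2 to 18. It understates the Mullen, Bayley and 8.4.6 DQs by 1.45% to 1.57%, which is about 0.44 to 0.47 points at a true DQ of 30 and 0.87 to 0.94 points at a true DQ of 60. The age figures assume a mean month of 30.4375 days. The DQ figures also assume that age equivalents are in calendar months.

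The Vineland DQ is outside this conclusion because it is not recomputed. Whether the redacted exploratory endpoints use the affected DQs cannot be determined from the public documents.

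**What to change.** In SAP 8.4.1, set chronological age in months to (testing date − date of birth)/30.4375, and derive the Mullen, Bayley and 8.4.6 DQs from it. Exact calendar months would serve equally well, provided one method is used throughout.

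Two checks should go with the change:

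- Confirm from the scales' scoring material that the age equivalents are in calendar months, then state that unit in section 8.4.
- Confirm how age was computed for the Vineland DQ on the CRF, so that all quotients share one age basis or the difference is noted.

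The cost is one constant and the removal of one added day in the SAP and the derivation program. Both dates are already inputs, so no new data are needed. SAP section 1 already allows justified deviations that are documented in the clinical study report.
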